### **Purpose.**

Understanding what behaviors will support cognition into late adulthood has become a major public health issue as the baby boomer generation enters old age. At present, there are no effective drugs for Alzheimer's Disease (AD), and clinical drug trials continue to fail. However, the Alzheimer's Association estimated in 2015 that delaying the onset of symptoms by 5 years would reduce the rate of incidence by 50 percent. Hence, it has become increasingly urgent to investigate other avenues that might delay the onset of symptoms. It is widely believed that maintaining an active lifestyle is important for maintaining cognitive health with age. Current methods of measuring whether engagement is protective of cognition in late adulthood are largely based on observational studies. These types of studies, however, limit the isolation of cause-effect relationships and the identification of what aspect of engagement is driving the enhancement of cognition.

Scientific evidence that engagement is protective of cognition in late adulthood is largely based on observational studies. The use of observational studies, however, limits both the ability to isolate cause-effect relationships and to determine what aspect of engagement is driving the enhancement of cognition. In a previous study (the Active Interventions for the Aging Mind or AIM study – approved by UTSW IRB #072010-144), we developed an experimental design that allows us to infer causality that sustained engagement in mentally challenging activities enhances or maintains cognition in older adults. In Phase I of the original AIM study (conducted from 2008 to 2012), participants were placed in one of six conditions in which novice subjects learned to quilt, learned to use digital photography, learned a combination of the two, engaged in social activities, engaged in workbooks at home, or experienced no intervention. During their time in the intervention, participants spent five hours each week in structured courses with professional instructors engaging in their activity and an additional ten hours working on their skill with others and without instruction. Subjects who completed the behavioral testing and who, through screening, volunteered and were eligible to participate completed MRI imaging both pre- and post-intervention in which they completed two fMRI tasks. This AIM study found both the photography and quilting groups displayed significant benefits in their ability to remember personal events and episodic memory when compared to the social and placebo group, the photography group experienced the most significant benefit to cognition, especially regarding memory functioning (Park et al., 2014). The photography and quilting engagement groups also experienced increased neural modulation (Park et al., 2014), which is correlated with more efficient use of neural resources – and less compensatory neural scaffolds – in older adults (McDonough et al., 2015).

We propose a study that would allow us to evaluate the effectiveness of engagement on cognitive function and determine whether mental effort is a contributing factor to changes in cognitive function. We plan to enroll 90 participants in the Impact of Challenging Engagement study and assign them to one of three groups: high-demand photography, moderate-demand photography, and active placebo. These initial groups will allow us to collect data and address the feasibility for converting the project into a full trial. Participants will engage in their different engagement conditions for 15 hours per week, based on successful results from the initial AIM study. In the Impact of Challenging Engagement study, we expect to expand on the results of the AIM study to determine if high-demand activities result in any observable brain changes when compared to moderate demand or placebo activities. Behavioral and neural measures of cognitive change will be assessed, providing considerable insight into mechanisms of change. Subjects will be characterized thoroughly in terms of behavioral tests of cognitive function, and a subset of subjects who meet neuroimaging criteria will undergo an fMRI procedure.

### **Background.**

In the present study, we consider that cognitive engagement may lead to improved cognitive and neural function. In support of this hypothesis, Kempermann, Kuhn, and Gage (1998) demonstrated that old rats maintained in complex visual and play environments showed birth of new neurons in the hippocampus. Kobayashi, Ohashi, and Ando (2002) reported improved learning ability in rats exposed to an enriched environment, even in old age, and concluded, "These results show that aged animals still have appreciable plasticity in cognitive function and suggest that environmental stimulation could benefit aging humans as well." Kempermann, Gast, and Gage (2002) reported a similar effect and demonstrated that short-term exposure of rats to an enriched environment, even in old age, led to five-fold increase in hippocampal neurogenesis, as well as a decrease in age-related atrophy in the dentate gyrus. The authors make a direct link of their findings to human behavior and ask, "Could this plastic response be relevant for explaining the beneficial effects of leading an 'active life' on brain function?" There is strong evidence that intellectually challenging environments and physical activity impact favorably upon human cognition during late adulthood. For example, Schooler et al. (1999) reported that engagement in "substantively complex" work, which would require the development of new schemas and change of existing ones across the lifespan, predicted better intellectual functioning in old age than engagement in less challenging work, even after education and other related factors were controlled. Other evidence in support of the productive engagement hypothesis comes from the Maastricht Longitudinal Study. At the beginning of the study, none of the participants enrolled (aged 50 to 80) showed cognitive impairment, but three years later, 4% of those with low cognitively demanding jobs showed some cognitive

impairment, whereas only 1.5% of those with mentally demanding jobs were impaired (Bosma et al., 2003). Overall, we found 13 studies in the literature that assessed the impact of jobs that varied in demands on cognitive function. Of these 13 studies, all but one showed a positive impact on cognition, with more demanding work resulting in better cognitive function.

Next, we examined studies that assessed the impact of engaging in cognitively demanding activities such as reading, playing bridge, or doing crosswords puzzles. We found a total of 13 such studies. Of these, nine showed positive effects, either in terms of improved cognitive function measured in the laboratory or a delay in the onset of dementia. We note here that many of these activities are relatively low in their cognitive demands, such as playing games or even listening to the radio or watching television, and would qualify as forms of receptive engagement. Then, we isolated studies that involved the impact on cognitive function of engagement in a combination of both leisure and cognitive activities. Of these studies, all but one demonstrated an enhancement effect, suggesting that breadth of experiences may be important in supporting cognitive function. Finally, we found five studies that examined the impact of exclusively social engagement on cognition or incidence of dementia, and all of these showed a positive impact of social engagement on cognition. Our examination of the literature makes it clear that there is experimental evidence in animals that engaging environments result in enhanced neural structure and function in old age, while correlation studies of humans overwhelmingly indicate that productive engagement (and sometimes even receptive engagement) across the lifespan is related to higher cognitive function and resilience in the face of mild levels of brain disease.

The Impact of Challenging Engagement project is a bridge from the animal to the human data, as it provides a mechanism to create different types of engagement environments and to determine experimentally if such engagement enhances cognitive function.

### **Concise Summary of Project.**

In the proposed research, we will enroll a total of 90 subjects over 16 weeks. Just as in the original AIM study (approved by UTSW IRB #072010-144), subjects will be randomly assigned to participate in one of 3 conditions with 30 subjects per group. Two of the groups involve active intellectual engagement. In these groups, novice subjects will engage in high-demand or moderate-demand photography in five hours of structured courses with professional instructors for each of the 16 weeks. Subjects will also be required to put in an additional investment of 10 hours each working on a project to which they can apply their learned skills. Subjects are expected to be working on their projects for a total of 210 hours of engagement over the 16 weeks. We will measure pre/post change in multiple measures of cognitive and neural function, affect, and activity over the 16 weeks, and contrast change with one control group. The control group, the Placebo Control, will engage alone at home in tasks that are relatively low in intellectual engagement such as listening to music and radio or completing work-books that rely primarily on activation of knowledge. Preliminary data collected at the University of Illinois has indicated that volunteers willingly engage in a similar program.

### **Study Procedures.**

This study takes place over 16 weeks and is broken down into pre-testing (weeks 1-2), intervention (weeks 3-16), and post-testing (weeks 15-16).

### **Participant Recruitment**

90 subjects will be recruited to participate in this study that lasts 16 weeks. Subjects will participate in one of 3 conditions with 30 subjects per group. Two of the groups involve active intellectual engagement. In these groups, novice subjects will engage in high-demand or moderate-demand photography in five hours of structured courses with professional instructors for each of the intervention weeks. The third group consists of an active placebo group that will engage in cognitively demanding activities at home (like completing crosswords and listening to music).

### **Pre-Intervention Testing (Weeks 1-2)**

**Cognitive Battery:** Participants will complete consent forms, vision screening, and cognitive tasks including assessment for episodic memory, executive function, inductive reasoning, working memory, verbal fluency, speed of processing, and crystallized intelligence. The cognitive session will last around 3 hours in total. Details of the cognitive battery participants will complete during this period can be found in Appendix A.

**Take-Home Questionnaires:** Self-reported questionnaires are completed by the participants on their own by logging into our website. Login information will be e-mailed to participants immediately following the pre-test cognitive battery. Participants may log in and out to complete the questionnaires at their own pace, but if they choose to complete all questionnaires in one sitting, it will take approximately 160 minutes in total. See Appendix A for the list and description of the questionnaires.

**Neuroimaging:** Participants who meet the MRI screening requirements will be given the option of completing the MRI battery. MRI scanning will last approximately 75 minutes and include both structural and functional scans. Details of the MRI scans can be found in Appendix A.

### **Intervention (Weeks 3-16)**

Subjects will be pseudo-randomly assigned to intervention groups (based on gender and education criteria and the needs of the study) and then will participate for at most 14 weeks in the manipulation to which they were assigned. All will be told that there are numerous studies in the literature suggesting that the condition to which they were assigned is a form of engagement that has been shown to improve cognition. This is true, as many correlational studies have shown that engagement in tasks as passive as watching television is related to better cognition. All subjects will be required to agree to participate in any of the three conditions so that no condition will be biased. They will be novices at the use of the digital camera and will have had only minimal experience with computers, , or digital photography. Subjects who use traditional cameras will be permitted to enroll.

**Productive Engagement Groups.** (High-Demand and Moderate-Demand Photography) Sixty total participants will be assigned to one of the productive engagement groups (with thirty participants in each group): high-demand photography, and moderate-demand photography. Before the intervention begins, subjects will be provided equipment appropriate to their intervention for them to loan throughout the 12- to 14-week intervention. Participants in either of the photography groups will be supplied digital cameras. These 30 participants in each group may be separated further into smaller sections based on instructor availability in order to take advantage of smaller class sizes.

Each group will meet for 2.5 hours twice a week (5 hours per week total) at the research site. During this time, subjects will be stepped through a detailed curriculum by professional instructors, and those who learn techniques quickly will be pushed along so that maximum new learning occurs for each subject. Additionally, all subjects will be required to spend an additional 10 hours working on a special project at the research site without any formal instruction. This project is meant to provide participants with an opportunity to apply their skills to a task as they are learning. The high-demand photography group will learn similar skills as the moderate-demand photography group, but will learn them at a significantly quicker pace and, therefore, will learn more skills by the end of the intervention than the moderate-demand group.

Based on our experience, we find that the final week of the interventions can be very busy and that some subjects experience somewhat lower affect in the last week due to their regrets that the class is ending. To ease this problem, we offer all subjects the opportunity to continue to work for at least two more weeks after the formal 12-week class is over, and subjects are paid sufficiently well to allow them to purchase a camera, should they desire to continue their work. Additionally, many subjects make plans for continued social relationships among group members.

**At-Home Engagement Group (Placebo Control).** Thirty subjects will be assigned to this group. Each participant will be given a personal DVD player, if they do not have one already, to borrow while they are enrolled in the study. Each week, subjects will come to the lab to maintain contact with the researchers and receive a new set of materials to work on that week. Subjects will be supplied with a range of stimulating activities to complete each week at home.

Subjects will have five hours of required activities each week and will select an additional 10 hours of activities of their choice from a provided list. For the five required hours, subjects will (1) watch 1 hour of humorous programming, (2) watch 1 hour of educational programming, (3) read 1 hour of an educational magazine, (4) listen to 1 hour of classical or world music, and (5) complete 1 hour of puzzle games that rely on activation of existing knowledge (such as crossword puzzles or handheld games). Subjects will then select the additional ten hours of activities which include (1) 2 hours of watching humorous programming of their choice, (2) 2 hours of watching educational programming and reading educational material, (3) 2 hours of listening to music CDs, (4) 2 hours of completing paper and pencil or handheld games, and (5) 2 hours of watching classical programming of their choice including Oscar-winning movies and movie classics. All participants will answer simple questions about the amount of time they spent on each task, how well they liked each task, and how it made them feel, including questions about whether it made them feel more alert.

**Subject Diaries.** Subjects from all three groups will keep detailed diaries of their behaviors over weeks 3 through 14, describing not only how much time they spend on the project activities, but also the time spent on outside activities. The instructors/group leaders will also complete weekly assessments of subjects' level of engagement and activity level.

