For phone signup: Participants will call in and receive the initial screening form over the phone. For those who are deemed ineligible based on this screening, participants will be informed immediately. For those who may be eligible, research staff will inform participants that they will receive a second phonecall within 48 hours/2 business days for a potential second screening. At this second screening, participants will be administered the TICS screening, and be given information about upcoming informational meetings. They will also be invited to fill out the enrollment form, either online or via email. Interested individuals will attend the informational meetings and learn about the logistics of the study, the time commitment, randomization of group assignment, compensation and criteria for potential participants, as well the minimal risks associated with each condition. These meetings are meant to educate a potential pool of participants who, after the meeting, may be screened and eligible to be enrolled in the study. The sustained nature of the commitment to the project will be explained to subjects. Those volunteers who meet the inclusion/exclusion criteria and are interested in participation after learning more will be provided with a detailed consent form by trained laboratory personnel. Written consent will be obtained. Additionally, individuals who participate in the behavioral portion of this study will also be screened for the MRI portion of the study. If subjects meet the MRI criteria, they may be invited to participate in an fMRI session, in addition to the behavioral component for which they have already qualified.

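### The allocation rule lets an undefined study need help decide the arm, with no sequence generation or concealment, in a trial described elsewhere as randomised

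*Combined protocol and SAP*

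**What the plan says.** The Concise Summary of Project states that "subjects will be randomly assigned to participate in one of 3 conditions with 30 subjects per group". Under Recruitment of Subjects, volunteers at the information meetings "learn about the logistics of the study, the time commitment, randomization of group assignment". The rule itself stands under Intervention (Weeks 3-16): "Subjects will be pseudo-randomly assigned to intervention groups (based on gender and education criteria and the needs of the study". The same paragraph offers one safeguard: "All subjects will be required to agree to participate in any of the three conditions so that no condition will be biased".

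The SAP (Analysis of Primary Outcome Variables) lists center, age, sex and education as stratification factors, but uses them only in secondary models. The primary cognitive ANCOVA contains baseline score and arm. The SAP's subgroup section names Dallas and Hamburg as centers, whereas the Intervention section describes classes at a single research site.

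The text available for review does not say how a sequence is generated, who holds it, when the arm is revealed, or what the study's needs are.

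**The concern.** The gender and education part of the rule can be read as stratified randomisation, and the SAP's wording supports that. The third criterion cannot. It is an open-ended ground for placing a person in one arm rather than another, and nothing prevents the person doing the placing from knowing the participant.

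The Purpose section gives a feasibility aim, and feasibility counts do not depend on how the arms are formed. The Background, however, presents the project as an experimental test of whether engagement improves cognition, and the SAP specifies a primary treatment comparison. That comparison rests on random allocation. If motivated or readily available people are steered to one arm, the contrast is biased in a direction nobody can determine afterwards. Volunteers are also told something different from the rule that would be applied to them.

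**Working it through.** **1. Is discretion needed for any benign purpose?** Four readings of the third criterion were considered.

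- Equal arms ("Subjects will participate in one of 3 conditions with 30 subjects per group"): the sequence can fix this.
- The quotas for men and minorities in the inclusion criteria: these are met at enrolment, before an arm exists.
- Class logistics ("These 30 participants in each group may be separated further into smaller sections based on instructor availability"): this splits people inside an arm already assigned.
- Balancing MRI-eligible participants: this can be a named stratum.

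The stated safeguard, willingness to accept any condition, limits self-selection by participants. It does not limit choice by staff.

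**2. Timing.** Study Procedures describes the study as "broken down into pre-testing (weeks 1-2), intervention (weeks 3-16), and post-testing (weeks 15-16". Assignment is described under the intervention heading and participation follows it. Assignment after pre-testing is therefore an inference from the layout, though a natural one.

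**3. Scale of a possible bias.** The documents give no figure, so this shows scale only.

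- Standard error of a two-arm contrast, 30 per arm: √(2/30) = 0.258 residual SD.
- One person placed by choice, whose outcome differs by 1 residual SD from that of the person displaced: 1/30 = 0.033 SD, or 0.033/0.258 = 13% of the standard error.
- One direct swap between the two compared arms: 2/30 = 0.067 SD, or 26%.

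A simulation (6,000 trials per scenario) assumed a baseline-outcome correlation of 0.7, 65% female (from the SAP), education split 50/50, and gender and education explaining 10% of post-baseline variance. An unmeasured prognostic factor explained a share u of that variance. In a fraction d of allocation triplets, the better-prognosis person of two was sent to one particular arm. The mean absolute difference of two standard normals is 2/√π = 1.128, so the expected bias in outcome SD is d × 1.128 × √u × √(1 − 0.7²).

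| d | u | Formula | Simulated bias | Type I error, gender and education adjusted |
|---|---|---|---|---|
| 10% | 10% | 0.025 | 0.023 | 4.9% |
| 25% | 10% | 0.064 | 0.067 | 6.9% |
| 50% | 10% | 0.127 | 0.125 | 10.4% |
| 10% | 20% | 0.036 | 0.036 | 5.3% |
| 25% | 20% | 0.090 | 0.092 | 8.4% |
| 50% | 20% | 0.180 | 0.183 | 17% |

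The bias was the same, to within 0.001 SD, with gender and education in the model or left out. Adjustment does not remove it.

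**4. Equal arms without discretion.** Sort the tested list by stratum, shuffle within stratum, and run random blocks of three straight through. Then 90/3 = 30 blocks give exactly 30/30/30 every time. A stratum can cut one block at each end, so arm counts within it differ by at most 2. In 20,000 simulated lists both results held. Separate permuted blocks of 3 and 6 in four gender-by-education strata gave exactly 30/30/30 in 20.9% of lists and 28 to 32 per arm in 98.6%.

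**5. Leaving gender and education out of the ANCOVA.** If allocation balances the two factors and they explain a share R² of residual variance, omitting them inflates the standard error by about 1/√(1 − R²). Simulation (200,000 trials per value, whole-list scheme):

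| Assumed R² | SE ratio, omitted/included | Size, omitted | Size, included |
|---|---|---|---|
| 0% | 0.999 | 4.92% | 4.95% |
| 1% | 1.004 | 4.89% | 5.03% |
| 2% | 1.010 | 4.75% | 4.96% |
| 5% | 1.026 | 4.47% | 5.01% |
| 10% | 1.055 | 3.92% | 4.99% |
| 20% | 1.120 | 3.00% | 5.06% |

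In a time-by-treatment mixed model with complete data, main effects of the two factors leave the contrast unchanged. In one simulated dataset the standard error was 0.1937 without covariates and with main effects alone, and 0.1719 with factor-by-time terms.

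**The case against.** The strongest reply is that this is one vague phrase in a small study with a feasibility aim. Two other sections say random, the SAP speaks of stratification, and nothing shows that anyone was or will be steered. The bias may be zero. That is true, and the conclusion claims no more than that the rule permits steering. But the vague phrase is part of the operative rule, so this is more than missing detail, and the feasibility aim does not withdraw the planned treatment comparison.

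A second point is that outright deletion might discard a legitimate balancing factor, such as MRI eligibility. This stands in part: such a factor should be kept, but named as a stratum.

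A third is that parts of the SAP refer back to text not available for review, so a fuller allocation description may exist. That tempers the statement that the method cannot be determined. It does not cure a complete sentence that contradicts two others.

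Finally, the covariate gain rests on assumed R² values and is slight at the low end, and the description of it as precision only holds only if the arms really are balanced on the two factors. Both are accepted. The center mismatch is a wider inconsistency and matters here only because center is listed as a stratification factor.

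**Conclusion.** The concern holds. As written, the rule permits non-random assignment, probably after pre-testing, with no described sequence or concealment, and it conflicts with two statements that assignment is random. The size of any bias is unknown: zero without steering, and about 0.02 to 0.18 SD across the assumed scenarios, of either sign. The importance does not rest on those figures. It rests on the defect being beyond repair by the planned adjustment once arms are formed and cheap to remove beforehand. It must be corrected before allocation.

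The covariate point is secondary. Given balanced allocation, omission makes the test conservative and loses precision (standard error 0.4% to 12.0% too large for R² of 1% to 20%). It does not add false positives.

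**What to change.** **Allocation.** In the Intervention section, delete the third criterion; if it stands for a real balancing factor, name that factor. State a computer-generated 1:1:1 allocation stratified by gender and education, with the categories written out. It should be produced by someone who neither enrols nor tests participants and concealed until that person's pre-testing is complete.

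- If participants enter as one tested cohort, use the whole-list scheme in step 4.
- If entry is staggered, use concealed permuted blocks within strata and change the fixed 30 and sixty to approximate numbers in the Concise Summary, Participant Recruitment and both group descriptions.

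**Consistency.** Make the Concise Summary, Recruitment, Intervention and SAP agree on method and factors. Age can remain in the SAP as an ordinary baseline covariate. If there are two centers, allocate within center and keep it as a factor. If there is one, remove center from the SAP, since a constant term cannot be fitted.

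**Analysis (secondary).** Add gender and education, and center if there are two, to the primary ANCOVA. Add them as factor-by-time terms wherever a time-by-treatment mixed model is used.

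**Cost.** A short script, one protocol sentence and matching edits, with no extra participants. No extra staff are needed if a suitable independent person already exists, which the documents do not show. Staff lose discretion over arm; splitting an arm into class sections is unaffected. With 90 complete, the ANCOVA has 84 residual degrees of freedom instead of 86 (83 with center). Main and by-time terms in the four-region brain model add 2 × 2 × 4 = 16 parameters (3 × 2 × 4 = 24 with center), which weighs more in the smaller MRI subset. Under staggered entry, arms will usually not be exactly 30.
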